### 2.1.3 Dose-Limiting Toxicities

The DLT observation period is 15 days from date of first (W1D1) CMP-001 injection (i.e., following 3 doses of CMP-001; W1D1, W2D1, W3D1). Subjects who have received at least one dose of CMP-001 and pembrolizumab are evaluable for DLT assessments.

DLTs are defined below and only include AEs that are considered possibly, probably, or definitely related to the CMP-001 plus pembrolizumab combination. Attribution of AEs specifically to either CMP-001 or pembrolizumab is challenging, therefore, the relationship to CMP-001 should be based on attribution to the combination of the two study drugs (CMP-001 + pembrolizumab).

The following AEs will be considered DLTs **if deemed related to study drug combination**:

- Hematologic
  - Grade 4 neutropenia
  - Febrile neutropenia, defined as absolute neutrophil count (ANC) <1000/mm^3 with a temperature of  $\geq 38.3$  degrees C
  - Grade  $\geq 3$  neutropenic infection
  - Grade  $\geq 3$  thrombocytopenia with clinically significant bleeding seeking medical intervention
  - Grade 4 thrombocytopenia
- Non-hematologic:
  - Grade  $\geq 3$  toxicities (non-laboratory); excluding:
    - Grade 3 fatigue lasting <7 days
    - Grade 3 arthralgia or myalgia that downgrades to less or equal to grade 2 within 3 days of supportive care
    - Grade 3 pain at injection site that downgrades to less than or equal to Grade 2 within 3 days of supportive care

- Grade 3 electrolyte abnormalities that are asymptomatic and reversed with medical intervention within 3 days
  - Grade  $\geq 3$  nausea, vomiting or diarrhea despite maximal medical intervention
  - Grade 4 aspartate aminotransferase (AST) and alanine aminotransferase (ALT) unless alternate explanations such as viral hepatitis or disease progression in the liver
- Other (non- AST/ALT) non-hematologic Grade  $\geq 3$  laboratory value if the abnormality leads to overnight hospitalization

[figure not shown]
[figure not shown]
**IMPORTANT:** CMP-001 activates plasmacytoid dendritic cells (pDC) through agonism of TLR9. Upon activation by CMP-001, pDCs will induce large amounts of interferon and TH1-promoting cytokines. Therefore, it is expected that toxicities associated with CMP-001 dosing may resemble interferon-related toxicities as well as symptoms associated with cytokine release such as chills, rigors, fever, nausea/vomiting, flu-like symptoms and/or hypotension which may present hours after CMP-001 injection. **Therefore, AEs such as headache, chills, rigors, fever, nausea/vomiting, flu-like symptoms and/or hypotension that are Grade 3 and below AND resolved to Grade 1 or below within 24 hours with standard supportive care will not be considered a DLT.** All toxicities regardless of grade should be managed according to standards of care and reported as AEs.

An AE believed by the Investigator to be caused by tumor flare or pseudoprogression does not necessarily need to be considered a DLT. Any such cases that would otherwise meet DLT criteria must be discussed immediately with the Medical Monitor. If the Investigator, Medical Monitor, and Sponsor agree that tumor flare is a likely explanation for the AE, treatment with CMP-001 may continue as long as the subject is closely monitored by the Investigator or study staff while on study.

Subjects who experience a DLT will have CMP-001 and pembrolizumab dosing withheld until the toxicity has returned to  $\leq$  Grade 1. If the Investigator determines that continued treatment with CMP-001 is in the subject's best interest, treatment of CMP-001 may resume at a reduced dose, one dose level lower than the subject's current dose at the same schedule after consultation with the Sponsor. Only one dose reduction is allowed. Subjects who continue to experience DLTs must come off study. If a CMP-001 injection is delayed due to toxicity, including a DLT, it should be given as soon as possible once the toxicity has resolved.

The Investigator may escalate the subject back to the original dose level if: 1) the lower dose level was tolerated without any DLTs; 2) Sponsor approval is given.

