**Table 1b. Decision table to choose Case A, B, or C to determine the dose assignment for new patients**

**A maximum of 21 patients will be treated sequentially in up to 7 cohorts of three patients each. Treatment will start in the first cohort at a CMP-001 dose of 7.5 mg. After a cohort is evaluable for efficacy and dose-limiting toxicity (DLT), the next cohort will be treated at the admissible dose with highest mean utility.** Admissible dose levels ( $j$ ) are determined according to the following posterior probability criteria for their true rates of DLT ( $\pi_{T,j}$ ) and efficacy ( $\pi_{E,j}$ ):

$$\Pr(\pi_{T,j} > 0.3 | data) < 0.925$$

$$\Pr(\pi_{E,j} < 0.5 | data) < 0.90.$$

Desirable tradeoff between treatment benefit and risk is quantified with a utility function defined by the investigators to be  $\Pr(\pi_{E,j}) - 0.3 \Pr(\pi_{T,j})$ . If a dose is found to not meet the admissibility criteria during the trial, it will be eliminated from further enrollment. If the number of patients at the current dose reaches 12, the trial will be stopped. Specifically, dose selection in the BOIN12 design proceeds according to the following 3 steps.

1. Treat the first cohort at dose level  $j = 1$ .
2. Suppose that the current dose level is  $j$ , use decision Table 1a to choose one of the following three cases to determine the dose for treating the next cohort of patients.

**Case A:** Determine the desirability of dose levels  $j - 1$ ,  $j$ , and  $j + 1$  using the rank-based desirability scores (RDS) given in Table A of APPENDIX F, and choose the one that has the highest desirability to treat the next cohort. If the RDS of all three doses are “E,” stop the trial and no dose should be selected. In the case that dose level  $j - 1$  or  $j + 1$  does not exist, then apply the above rule to dose levels  $j$  and  $j + 1$  (or  $j$  and  $j - 1$ ).

**Case B:** Determine the desirability of dose levels  $j$  and  $j - 1$  using the RDS given in Table A of APPENDIX F, and choose the one that has the higher desirability to treat the next cohort. If the RDS of the two doses are “E,” stop the trial and no dose should be selected. If the current dose level  $j$  is the lowest dose, treat the next cohort of patients at the lowest dose unless the RDS of the lowest dose is “E,” at which point terminate the trial.

**Case C:** Determine the desirability of dose levels  $j$  and  $j - 1$  using the RDS given in Table A of APPENDIX F.

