#### **4.1.1 Preclinical and Clinical Trial Data on CMP-001**

##### **4.1.1.1 Advanced Melanoma study (NCT02680184)**

Intratumoral administration of CMP-001 is currently being evaluated in combination with pembrolizumab in subjects with advanced melanoma resistant to checkpoint inhibitors.

In study CMP-001-001, A Multicenter, Open-label Phase 1b clinical Study of CMP-001 in Combination with Pembrolizumab in Subjects with Advanced Melanoma, CMP-001 is being administered IT on a weekly (Schedule A) and every 3 weeks (Q3W) (Schedule B) schedule across a dose range of 1-10 mg. To date, approximately 45 subjects have been treated in the CMP-001-001 study. Preliminary analysis of safety demonstrates an acute toxicity profile that predominantly consists of Grade 1-2 AEs associated with cytokine release including mild fever, chills, rigors, nausea, vomiting and occasional hypotension. In some subjects, the severity of this AE profile is increased. These AEs typically present after the third CMP-001 dose and generally resolve within a few hours with standard supportive care. A treatment algorithm has been developed for the management of these reactions and can be found in Section 6.2.1. CMP-001-001 AE summary of the Dose Escalation Phase are presented in Table 2.

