Subjects discontinuing study treatment earlier than planned or withdrawing from the study should undergo the End of Treatment (EOT) clinical and laboratory assessments (see Section 7.0 TRIAL FLOW CHART) as soon as possible after study treatment is stopped. The required 30 day follow-up phone call should also be completed. The reason for withdrawal will be recorded in the electronic case report form (eCRF) and the subject's source medical record.

If a subject withdraws from the study prior to completion of the 21 day assessment period for a reason other than a DLT, then a replacement subject will be enrolled at that dose level.

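### The 15-day DLT period closes on or about the day of the third CMP-001 dose, and it conflicts with the 21-day period and replacement rule in Section 5.5, so the toxicity count for Table A is not uniquely defined.

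*Combined protocol and SAP*

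**What the plan says.** Five statements in the combined protocol and SAP bear on this point.

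- **Length of the period (Section 2.1.3).** "The DLT observation period is 15 days from date of first (W1D1) CMP-001 injection". The same sentence explains the period as "following 3 doses of CMP-001; W1D1, W2D1, W3D1".
- **Who is evaluable (Section 2.1.3).** "Subjects who have received at least one dose of CMP-001 and pembrolizumab are evaluable for DLT assessments". No minimum follow-up is required.
- **Replacement (Section 5.5).** A new subject is enrolled at the same dose level in this case: "If a subject withdraws from the study prior to completion of the 21 day assessment period for a reason other than a DLT".
- **Expected timing of reactions (Section 4.1.1.1, melanoma study).** "These AEs typically present after the third CMP-001 dose and generally resolve within a few hours with standard supportive care".
- **Cohort decision (Section 2.1.2, text under Table 1b).** "After a cohort is evaluable for efficacy and dose-limiting toxicity (DLT), the next cohort will be treated at the admissible dose".

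The Trial Flow Chart gives the weekly visits from W2D1 to W7D1 a ±2-day window and puts the first scheduled response scan at W7D1. Table A of Appendix F, which drives every dose assignment, counts evaluable patients and those among them with toxicity.

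**The concern.** The DLT count is the toxicity input to both the admissibility rule and the desirability score. Two features of the text leave that count uncertain.

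First, the period is meant to follow three doses but ends at about the time the third is given. The protocol's own experience is that reactions typically appear after that dose. A compliant third injection can fall outside the period altogether.

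Second, two different periods and two different rules apply to a patient who leaves early without a DLT. One rule keeps the patient in the denominator with no toxicity. The other replaces the patient. With cohorts of three, one patient decides which row of Table A is read. If early leavers are kept, or third-dose events are missed, the count errs towards too little toxicity.

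**Working it through.** **1. Calendar.** Day of week w, Day 1 = 7(w − 1) + 1. This gives W1D1 = Day 1, W2D1 = Day 8, W3D1 = Day 15, W4D1 = Day 22 and W7D1 = Day 43. The stated 15 days is therefore the scheduled day of dose 3. The text does not say whether W1D1 is counted, so the period closes on Day 15 (W1D1 as Day 1) or Day 16 (15 elapsed days).

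**2. Days of follow-up after dose 3** = closing day − day of dose 3.

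| Dose 3 given on | Close Day 15 | Close Day 16 | Close Day 21 |
|---|---|---|---|
| Day 13 (2 days early) | 2 | 3 | 8 |
| Day 15 (on schedule) | 0 | 1 | 6 |
| Day 16 | outside | 0 | 5 |
| Day 17 (2 days late) | outside | outside | 4 |

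Section 2.1.3 and flow chart footnote m also allow a dose to be delayed for toxicity, so dose 3 can fall later than Day 17. The DLT exclusions in Section 2.1.3 use resolution times of 24 hours, 3 days and (for fatigue) 7 days. After an on-schedule dose 3, at most the first of these fits inside the 15-day period.

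**3. The same patient under the two sections.** Assume each has had one dose of both drugs and no DLT.

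| Patient leaves on | Section 2.1.3 | Section 5.5 |
|---|---|---|
| Day 10 | DLT-evaluable, no DLT | replaced |
| Day 18 | period completed, no DLT | replaced |

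**4. Effect on Table A.** Take a first cohort in which two patients have a DLT and the third leaves on Day 10. Table A does not state a prior, so assume a uniform one.

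- 2 of 3 with DLT: posterior Beta(3,2). Pr(rate > 0.3) = 1 − (4 × 0.3³ − 3 × 0.3⁴) = 1 − 0.0837 = 0.916. This is below 0.925, so the dose stays. Table A agrees (RDS 27, 53 or 80 for 1, 2 or 3 responses).
- 3 of 3 with DLT: posterior Beta(4,1). Pr(rate > 0.3) = 1 − 0.3⁴ = 0.992. This is above 0.925, so the dose is eliminated. Table A agrees (E).

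Keeping the leaver fixes the row at 2 of 3. Replacing the leaver gives 2 of 3 or 3 of 3, depending on the new patient. A third-dose DLT missed because the injection fell on Day 17 causes the same one-row shift.

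**5. Sensitivity of selection to the captured rate.** From Table B, efficacy 0.5 at both doses, adding the two selection percentages:

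- DLT 0.20 (Scenario 6): 52.3 + 38.2 = 90.5%
- DLT 0.30 (Scenario 8): 53.9 + 22.9 = 76.8%
- DLT 0.40 (Scenario 10): 44.8 + 9.1 = 53.9%

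The documents give no fraction of DLTs that the period would capture. Purely as an illustration, take a true rate of 0.40. Capturing all of it, three quarters (0.30) or half (0.20) corresponds to 53.9%, 76.8% or 90.5% selected.

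**6. Time.** The first scheduled scan is on Day 43. Section 8.1.3 allows it up to five days early, on Day 38. Either way it comes at least 17 days (38 − 21) after a Day 21 close.

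**The case against.** Much can be said for the plan.

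- The parenthesis in Section 2.1.3 makes the intent clear. Reactions arise within hours, and Section 6.1.2.7 requires at least four hours of observation after each of the first five doses. A reaction to an on-schedule third dose can be captured. Nothing says that an event starting inside the period must also resolve inside it to be classified. This stands for on-schedule doses. It does not help a dose given on Day 17 or later.
- Section 4.1.1.1 describes mainly Grade 1-2 events, and Section 2.1.3 exempts listed reactions of Grade 3 or below that settle to Grade 1 or below within 24 hours. Most of these reactions would not be DLTs under any period. The melanoma study also mixed weekly and three-weekly schedules, so its third dose is not always Day 15. Both points stand and limit the size of the loss.
- Section 5.5 does not call its 21 days the DLT period. However, its exception for DLTs makes sense only if it is the same assessment.
- A patient who leaves after the priming dose alone is evaluable under Section 2.1.3 only if pembrolizumab has also been given. Table 6 suggests Day 1 of each cycle, but inclusion criterion 8 separates priming from a therapeutic phase shown in a schema that is not in the available text. The conflict is therefore stated only for patients who have had both drugs.

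A reader might go further and infer that toxicity up to Week 7 is ignored, that an over-toxic dose would usually be selected, and that the Table A count must be cut at W7D1. The documents do not support this. Later toxicity is still recorded, cumulative events are reviewed under Appendix E, and Section 5.6 allows termination for adverse reactions. Any selection probability needs an assumed risk. Suppose 0.45 is spread evenly over intratumoral doses 2 to 7. Two doses then carry 1 − 0.55^(2/6) = 0.18. Dose 7 is given on W7D1 itself, so a cut there covers five doses: 1 − 0.55^(5/6) = 0.39. Interpolating Table B gives 76.8 − 0.92 × 22.9, or about 56%, against roughly 90% at the two-dose rate. That gap comes from the assumed 0.45 and the even spread, and the even spread sits poorly with reactions typically appearing after the third dose. A W7D1 cut would also change what the 0.30 limit and Table B mean.

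**Conclusion.** The passages are wrong as written and need reconciling. An on-schedule third dose has zero to one day of follow-up. A dose two days late, still within the visit window, has none. Sections 2.1.3 and 5.5 give opposite treatment to an early leaver without a DLT, and one such patient can decide between keeping and eliminating a dose.

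The calendar finding rests on the flow chart alone. The conflict rests on reading the 21 days as the DLT assessment period. How far the DLT count is understated cannot be computed from the documents, and Table B shows only that selection is sensitive to it. Table B is not in error: it describes whatever DLT rate the period captures. A short DLT period is a legitimate design choice, and extending it to Week 7 is not required by this finding.

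**What to change.** 1. Reconcile the 15-day and 21-day passages into one DLT period, used in both sections. Anchor it to the actual date of the third dose, or otherwise allow for the visit window, so that it covers the third-dose reaction period the protocol intends. State whether W1D1 counts as Day 1. The length is for the sponsor and investigator to set.
2. Define DLT-evaluable for Table A as having a DLT or completing that period, and make the replacement rule refer to the same definition. Apply it also to patients already treated at 7.5 mg who count towards the 21.
3. Optionally, tabulate related toxicity from the end of the period to W7D1 by dose as supporting information at each cohort decision. Making it the Table A count is a separate design choice and would need the 0.30 limit to be re-justified.

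The cost is protocol wording. No scheduled time is added, provided that response is judged at the scheduled W7D1 scan. The Week 7 timing is inferred from the cohort rule and the flow chart, and an unscheduled earlier assessment could shorten it. The downside is a slightly higher observed DLT rate and the occasional replacement of an early withdrawal, which Section 5.5 already foresees. Section 2.1.3 ties DLT status to treatment decisions, so the amendment should say whether the reconciled period affects those or only the Table A count.

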## 2.0 TRIAL DESIGN

### 2.1 Investigational Plan

#### 2.1.1 Overall Study Design

This is a single center, open-label, combined Phase I/II clinical study of intratumoral administration of CMP-001 and intravenous administration of pembrolizumab in selected subjects with lymphoma. The key study objective is to find a CMP-001 dose (**vidutolimod**) that in combination with pembrolizumab has optimal clinical efficacy and acceptable toxicity. Dose-finding will be performed with an adaptive clinical trial design. Secondary study objectives include characterization of safety, pharmacodynamics, and assessment of anti-lymphoma activity.

Each treatment cycle is 3 weeks in duration. The first CMP-001 injection stimulates antibody formation to the VLP of CMP-001 and will be given subcutaneously. Subsequently, CMP-001 will be administered by intratumoral injection every week for seven doses. The seventh dose, which is to be administered on Week 7 Day 1 (W7D1), represents the start of dosing at 3-week intervals (ie, with subsequent CMP-001 doses to be administered on Week 10 Day 1 [W10D1] and Week 13 Day 1 [W13D1]). Subjects enrolled into this study will continue study treatment so long as they do not experience unacceptable toxicities and in the Investigator's

opinion continued treatment is in the subject's best interest. Patient will be evaluated for treatment efficacy and toxicity up to 30 days after end of treatment and followed for long term survival for 2 years.

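### A patient counts as DLT-evaluable after one CMP-001 dose plus pembrolizumab, so patients who stop or delay CMP-001 early but stay in the study enter Table A as having no DLT

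*Combined protocol and SAP*

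**What the plan says.** Section 2.1.3 sets the window: "The DLT observation period is 15 days from date of first (W1D1) CMP-001 injection". It equates this with three CMP-001 doses, at W1D1, W2D1 and W3D1. The evaluability rule that follows asks for less: "Subjects who have received at least one dose of CMP-001 and pembrolizumab are evaluable for DLT assessments".

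Section 2.1.1 says what one dose is: "The first CMP-001 injection stimulates antibody formation to the VLP of CMP-001 and will be given subcutaneously". On the timing of cytokine-type reactions in the melanoma study, Section 4.1.1.1 says: "These AEs typically present after the third CMP-001 dose and generally resolve within a few hours with standard supportive care".

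Section 5.5 has a replacement rule, triggered as follows: "If a subject withdraws from the study prior to completion of the 21 day assessment period for a reason other than a DLT". A new patient is then enrolled at that dose level. The rule does not say whether the replaced patient leaves the DLT count. The same section treats stopping treatment while still being followed as a separate matter.

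Delays are provided for in Section 2.1.3: "If a CMP-001 injection is delayed due to toxicity, including a DLT, it should be given as soon as possible once the toxicity has resolved". Footnote m of the flow chart says no CMP-001 dose should be skipped and allows ±2 days for the weekly injections.

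Table A in Appendix F is indexed by the number of evaluable patients and the number of those with toxicity, so the evaluability sentence fixes both counts.

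**The concern.** The toxicity counts in Table A are the only toxicity input to the dose decisions, which serve the primary objective. A patient who had the prime and pembrolizumab, and whose second or third injection was delayed or never given, adds one to the denominator. That patient has had less opportunity to add to the numerator than the three-dose description implies. The observed DLT rate is then too low, and a dose that is too toxic is eliminated less readily.

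The two rules also conflict. A patient who leaves the study on day 10 without a DLT is evaluable under 2.1.3 and replaced under 5.5. Whether that patient is counted is left open, so two analysts could enter different rows of Table A from the same data.

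**Working it through.** **1. Reproducing Table A's toxicity limits.** Section 2.1.2 drops a dose when Pr(π_T > 0.3 | data) reaches 0.925. With a uniform Beta(1,1) prior (assumed), y DLTs in n patients give a Beta(1+y, 1+n−y) posterior. Each limit is matched:

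| n | Fewest DLTs eliminated | Pr | One fewer | Pr |
|---|---|---|---|---|
| 3 | 3 | 0.992 | 2 | 0.916 |
| 6 | 4 | 0.971 | 3 | 0.874 |
| 9 | 5 | 0.953 | 4 | 0.850 |
| 12 | 6 | 0.938 | 5 | 0.835 |

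The efficacy limits (0/3, ≤1/6, ≤2/9, ≤3/12) and the spot-checked desirability scores also match.

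**2. Removing under-exposed patients without a DLT.** Table A prints only n = 3, 6, 9 and 12, so the posterior rule is applied directly.

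- 2/3: 0.916, kept. One removed, 2/2: 1 − 0.3³ = 0.973, eliminated.
- 3/6: 0.874, kept. One removed, 3/5: 0.930, eliminated.
- 4/9: 0.850, kept. One removed, 4/8: 0.901, still kept. Two removed, 4/7: 0.942, eliminated.
- 5/12: 0.835, kept. One removed, 5/11: 0.882, kept. Two removed, 5/10: 0.922, kept.

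**3. Dilution of the rate.** Let f be the share of counted patients with no DLT risk. The documents give no value for f. The observed rate is π(1 − f). At π = 0.40:

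- f = 10%: 0.40 × 0.90 = 0.36
- f = 20%: 0.40 × 0.80 = 0.32

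**4. Effect on selecting a dose.** The design was re-simulated with 10,000 trials per scenario. Table 1b's decision table is not legible in the available text, so these settings are assumed: interval boundaries 0.236 and 0.359, a cut-off of N* = 9, final selection restricted to doses at or below the isotonic MTD, and independent DLT and efficacy outcomes.

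Against Table B, with efficacy 0.40/0.50, the chance of selecting some dose was:

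| DLT rate | Table B | Re-simulated |
|---|---|---|
| 0.20 | 35.8 + 48.8 = 84.6% | 83.6% |
| 0.30 | 40.3 + 29.5 = 69.8% | 67.4% |
| 0.40 | 35.3 + 11.9 = 47.2% | 44.2% |
| 0.50 | 21.3 + 3.0 = 24.3% | 22.6% |

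The match is close but not exact. The differences of 1.0 to 3.0 points are put down to the unknown settings, not to an error in the plan.

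Adding the dilution, the chance of selecting some dose becomes:

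| True DLT rate | f | Response unaffected | Also counted as non-responders |
|---|---|---|---|
| 0.40 | 0 | 44% | 44% |
| 0.40 | 5% | 49% | 46% |
| 0.40 | 10% | 54% | 47% |
| 0.40 | 20% | 63% | 48% |
| 0.50 | 0 | 23% | 23% |
| 0.50 | 10% | 33% | 28% |
| 0.50 | 20% | 44% | 31% |

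**5. The window and the third dose.** W3D1 falls 14 days after W1D1 and the DLT period is 15 days from W1D1. A patient dosed exactly on schedule has about 0–1 day of DLT observation after the third dose. With the ±2-day window, a compliant third dose can come up to 16 days after W1D1, which is after the period has closed.

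**The case against.** The case against has four parts.

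*Section 5.5 already handles the obvious route.* Someone who withdraws early without a DLT is replaced, and replacement ordinarily means the slot is refilled. This stands as a likely intention. It does not cover patients who stop or delay CMP-001 and stay in the study, and the text does not remove the replaced patient from the count.

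*Other safeguards apply.* Pembrolizumab is required, doses may not be skipped, and the next cohort waits for efficacy evaluability, with the first scan at W7D1. These reduce the problem without closing it. A dose that is not skipped may still be given after the window. The efficacy population in Section 9.3 also needs only one CMP-001 dose and one response assessment.

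*Under-exposed patients can still have a DLT.* This stands. Cytopenias, Grade 4 AST/ALT and other events attributed to the combination need no third dose. Many of the reactions in Section 4.1.1.1 would not be DLTs anyway: cytokine-type events are excluded when "Grade 3 and below AND resolved to Grade 1 or below within 24 hours with standard supportive care will not be considered a DLT". A patient delayed by toxicity has plainly reacted to treatment. Zero risk is therefore an upper bound on the effect.

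*A bare dose minimum would misfire.* This stands too. It could exclude compliant patients whose third dose fell after the window. Dropping patients delayed by sub-DLT toxicity would be informative exclusion.

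Two stronger readings are tempting. A reader might equate f = 25% (0.40 × 0.75 = 0.30) with a move from Table B scenario 9 to scenario 7, that is, from 47.2% to 69.8%. The documents do not support f = 25% or zero DLT risk, and the comparison leaves efficacy at 0.40/0.50 for patients who were barely treated. The shift nearly vanishes if they count as non-responders. A reader might also infer that patients held after the prime for lack of an anti-Qbeta response (inclusion criterion 8) enter the table. That depends on whether they have received pembrolizumab by then, which cannot be confirmed because the trial schema is not shown.

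**Conclusion.** The concern holds as a defect in the stated rule. The denominator of the toxicity count admits patients without the exposure the DLT period is said to cover, and Sections 2.1.3 and 5.5 conflict on who is evaluable and for how long. The direction of bias is downward wherever such patients carry less than the full DLT risk; its size cannot be stated, because the documents give neither their number nor their risk.

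The firm result is the fragility of early decisions: one patient can reverse an elimination in a group of three or six, and two can in a group of nine. At 12 patients, removing one or two changes nothing. The simulated rises in selection are illustrations. They rest on assumed values of f, zero DLT risk in those patients, and assumed software settings, and they are much smaller if the same patients count as non-responders.

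**What to change.** In Section 2.1.3, define a DLT-evaluable patient as one who either had a DLT in the window, or received pembrolizumab and the three CMP-001 doses the period is said to cover (allowing the visit windows) and completed observation.

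- Where toxicity delayed a dose, score the patient once the delayed doses have been given; do not exclude the patient. This costs little time, because the next cohort already waits for efficacy evaluability.
- Keep other under-exposed patients without a DLT in the safety summaries, leave them out of the patient and toxicity counts of Table A, and replace them.
- State in Section 5.5 that a replaced patient leaves the count.
- Reconcile 2.1.3 and 5.5 on the window: 15 against 21 days, and the fact that the 15-day period closes at about the third dose. A dose minimum alone does not resolve this.

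The cost is a few sentences in two sections and an occasional replacement patient.
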